2.3. Study Design

2.3.1. Overview of Study Design and Key Features

Overview of Study Design and Key Features	

The diagram illustrates the study timeline. It begins with a Screening phase from Study Week -2 to 0. At Week 0, Baseline/Randomization occurs. The Treatment Period follows from Week 0 to Week 26. At Week 26, the Primary Endpoint is reached. From Week 26 to Week 34, there is an Extension Study or Follow-up phase. Two treatment groups are compared: Group 1 receives Albiglutide active liquid autoinjector + placebo lyophilized DCC pen injector (N=150), and Group 2 receives Albiglutide active lyophilized DCC pen injector + placebo liquid autoinjector (N=150). The study includes participants with T2DM and HbA1c levels between 7% and 10%.
	

DCC dual chamber glass cartridge
 
 At baseline/randomization, albiglutide will be started at 30 mg once weekly with uptitration to albiglutide 50 mg once weekly at Week 4. Follow-up visit only for those subjects who discontinued investigational product (see Section 5.5), were withdrawn from the study, or who have completed the 26 week treatment period, but do not consent and/or are not eligible to participate in the 26 week extension study (Study 204682). 	
Design Features	
 Randomized, double-blind, multicenter, parallel-group, repeat-dose study of 26 weeks duration
Dosing	
 During the treatment period study treatment will be administered once weekly by subcutaneous (s.c.) injection in the abdomen, thigh, or upper arm. Study personnel will administer study treatment at clinic visits. Subjects will receive 30 mg of albiglutide for 4 weeks and will then be up-titrated to 50 mg albiglutide for the remaining 22 weeks of the study. Down-titration (dose reduction) of albiglutide from 50 mg to 30 mg is NOT permitted. If a subject experiences tolerability issues with the 50 mg dose then the subject may be withdrawn from the study at the discretion of investigator.
Treatment Assignment	
 Randomized treatment assignment will be done via the Interactive Voice Response System (IVRS) and randomization will be implemented based on a sequestered fixed randomization schedule. Approximately 300 subjects will be randomized for this study. Eligible subjects will be stratified by age (<65 or ≥65 years of age), weight (<90 kg or ≥90 kg), and background antidiabetic therapy (diet and exercise or stable dose of metformin). Subjects will be randomized in a 1:1 ratio to either: 1. Albiglutide active liquid auto-injector + placebo lyophilized DCC pen injector; or, 2. Albiglutide active lyophilized DCC pen injector + placebo liquid auto-injector.
Interim Analysis	
 No interim analysis is planned for this study.

2.3.2. Study Design

This is a phase III, randomized, double-blind, multicenter, parallel-group, repeatdose, study of 26 weeks duration to evaluate the efficacy, safety, tolerability and PD response of albiglutide liquid drug product relative to the commercial lyophilized drug product.

This study will comprise 3 study periods: screening (2 weeks), treatment (26 weeks) and for those subjects not entering the extension study a follow-up period (8 weeks).

The study will recruit subjects with T2DM who are failing to achieve optimal glycemic control on their current regimen of diet and exercise or stable dose of metformin. Subjects will continue on their current regimen for the duration of their participation in the study.

During the screening period, subjects will provide written informed consent and undergo procedures to determine eligibility for study participation. Screening will occur within 2 weeks of randomization.

At randomization, subjects will be stratified by age (<65 or ≥65 years of age), weight (<90 kg or ≥90 kg), and background antidiabetic therapy (diet and exercise or stable dose of metformin). Subjects will be randomized in a 1:1 ratio to either:

- Albiglutide active liquid auto-injector + placebo lyophilized DCC pen injector;

or,

- Albiglutide active lyophilized DCC pen injector + placebo liquid auto-injector.

Study treatment will be administered once weekly by s.c. injection in the abdomen, thigh, or upper arm. Study personnel will administer study treatment at clinic visits. Subjects will receive 30 mg of albiglutide for 4 weeks and will then be up-titrated to 50 mg albiglutide for the remaining 22 weeks of the study. Down-titration (dose reduction) of albiglutide from 50 mg to 30 mg is NOT permitted. If a subject experiences tolerability issues with the higher 50mg dose then the subject may discontinue investigational product (at the discretion of the investigator) and will be followed for safety and efficacy.

Subjects who completed the 26 week treatment period, did not discontinue investigational product, and meet all eligibility criteria may consent to participate in Study 204682, a 26 week extension study.

2.4. Statistical Hypotheses

The primary hypothesis to be tested is that the liquid drug product will provide glycemic control (as measured by HbA_{1c} change from baseline) non-inferior to the lyophilized drug product for a period of 26 weeks of treatment in subjects with T2DM.

- The null hypothesis is that the difference in the mean change from baseline to Week 26 in HbA_{1c} between the liquid drug product and the lyophilized drug product is greater than the non-inferiority margin of 0.4%.

- The alternative hypothesis is that the difference in the mean change from Baseline to Week 26 in HbA_{1c} between the liquid drug product and the lyophilized drug product is less than or equal to the non-inferiority margin of 0.4%.
- The null hypothesis will be tested based on the upper bound of 1-sided 97.5% confidence interval (equivalently, the upper bound of a 2-sided 95% confidence interval) of the least squares mean of the treatment difference estimated from a MMRM model. The MMRM model will include HbA_{1c} change from baseline as the dependent variable; treatment, region (defined in [Appendix 8: Multicenter](#)), age category (<65 or ≥65 years), weight category (<90 or ≥90 kg), background antidiabetic therapy (diet and exercise or stable dose of metformin), visit week, treatment-by-week interaction and baseline HbA_{1c}-by-week interaction as fixed effects; baseline HbA_{1c} as a continuous covariate; and subject as a random effect. An unstructured covariance matrix will be used for the MMRM analysis, unless the model does not converge, in which case the covariance matrix will be decided upon model convergence status and the Akaike information criterion. If the upper bound of 1-sided 97.5% confidence interval is less than or equal to 0.4%, non-inferiority will be concluded.

3. PLANNED ANALYSES

3.1. Interim Analyses

No interim analysis is planned for this study.

3.2. Final Analyses

The final planned primary analyses will be performed after the completion of the following sequential steps:

1. All subjects have completed the planned 26 weeks of study treatment or have completed participation in the study and the subsequent follow-up phase if applicable. For subjects who did not enter the extension study (Study 204682), they should complete the follow-up phase.
2. All required database cleaning activities have been completed and final database release and database freeze has been declared.
3. All criteria for unblinding the randomization codes have been met.

4. ANALYSIS POPULATIONS

Population	Definition / Criteria	Analyses Evaluated
Intent-To-Treat	
 Comprise of all randomized subjects who receive at least one dose of study treatment and have a baseline assessment. This population will be analysed according to randomly assigned treatment 	
 Efficacy
Safety	
 Comprise of all enrolled subjects who receive at least one dose of study treatment. This population will be analysed according to the treatment the subject actually received. 	
 Safety
Per-Protocol	
 Comprise of all randomized subjects who complete study procedures through Week 26 and are compliant with the protocol. This population will be analysed according to randomly assigned treatment. Protocol deviations that would exclude subjects from the PP population are defined in Section 4.1 (Protocol Deviations) and Appendix 1 (Protocol Deviation Management and Definition for Per-Protocol Population). 	
 Supportive analyses of the efficacy endpoints
Pharmacokinetic	
 Subjects in the Safety population for whom a pharmacokinetic sample is obtained and analysed. 	
 PK

NOTES :

- Please refer to [Appendix 14](#) List of Data Displays which details the population to be used for each displays being generated.

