9.3. Data Analysis Considerations

9.3.1. Analysis Populations

Intent-to-Treat (ITT) Population: The ITT Population will include all randomized subjects who receive at least 1 dose of the study medication and have a baseline assessment. The ITT population will be analyzed according to the randomly assigned treatment. The ITT Population is the primary population for all efficacy analyses.

Safety Population: The Safety Population is defined as all enrolled subjects who receive at least 1 dose of study medication. The subjects in the Safety Population will be analyzed according to the treatment received. The Safety Population will be used for all safety analyses.

Per-Protocol (PP) Population: The PP Population will include all subjects randomly assigned to treatment who complete study procedures through Week 26 and are compliant with the protocol. The subjects in the PP Population will be analyzed according to randomized treatment. The PP Populations may be used for supportive analyses of the efficacy endpoints.

Other analysis populations will be defined in the reporting and analysis plan (RAP).

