4.1. Protocol Deviations

- Significant protocol deviations (including deviations related to study inclusion/exclusion criteria, conduct of the trial, subject management or subject assessment) will be summarised by category and standard text description.
- Per-Protocol population is defined as all randomized subjects randomly assigned to treatment who complete study procedures on treatment through Week 26 and are compliant with the protocol. Significant deviations which result in exclusion from the Per-Protocol population will also be listed. (Please refer to [Appendix 1](#): Protocol Deviation Management and Definitions for Per Protocol Population).
- Protocol deviations will be tracked by the study team throughout the conduct of the study in accordance with the Study Deviation Rules document.

- Data will be reviewed prior to unblinding and freezing the database to ensure all significant deviations which may lead to exclusion from the Per-Protocol population are captured and categorised on the protocol deviations dataset.
- This dataset will be the basis for the summaries and/or listings of protocol deviations.
- All protocol deviations regardless of significance will be listed.
- A separate summary and listing of all inclusion/exclusion criteria deviations will also be provided. This summary will be based on data as recorded on the inclusion/exclusion page of the eCRF.

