6.6. Treatment Compliance

Study treatment (both active drug and placebo injector) will be administered to the subject by the site personnel in the clinic at each scheduled weekly visit from Week 0 (i.e. Baseline/Randomization), Week 1 through Week 25. At each scheduled weekly visit, study treatment administration status (Yes/No), date/time of dose administered (if Yes) and reason no dose administered (if No) will be recorded in the Exposure eCRF page.

Treatment compliance (in percentage) will be based on the Exposure eCRF page and calculated as total number of doses administered divided by total number of doses expected over all available scheduled visits on treatment. Treatment compliance will be summarized for all subjects, as well as for subjects who discontinue study treatment early and subjects who complete study treatment. Treatment compliance will be also categorized as < 80% and \geq 80%, and summarized descriptively by treatment group.

Individual subject compliance information will also be listed. All summaries will be performed using the safety population.

Acceptable overall compliance for IP (albiglutide liquid and lyophilized) in this study will be \geq 80%.

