11.1. Appendix 1: Protocol Deviation Management and Definitions for Per Protocol Population

11.1.1. Exclusions from Per Protocol Population

Final list of protocol deviations that lead to exclusion from Per-Protocol population will be determined by the study team and populated here toward the end of the study.

A subject meeting any of the following criteria may be excluded from the Per Protocol population based on clinical judgement in a case-by-case basis. In addition, other deviations that may not fall under the following criteria may be excluded from the per protocol population based on a case by case basis:

Number	Protocol Deviation Description
01	Concomitant Medication 
 Subject took medication prohibited by protocol (SAFETY) Subject took medication prohibited by protocol (EFFICACY)
02	Study Treatment Compliance 
 Subject did not receive \geq 80% of planned medication
03	Inclusion Criteria and Exclusion Criteria 
 Subject enrolled but did not meet all protocol inclusion criteria at screening. Subject enrolled but met exclusion criteria at screening.
04	Study Treatment Admin/Dispense 
 Incorrect study medication kit and/or pen dispensed to subject.
05	ICF (Informed Consent Form) Process/Timing 
 ICF(s) not obtained prior to any study procedure. Site staff did not sign and/or date ICF. Genetic blood sample collected without subject consent. ICF re-consenting issues/delays Incorrect ICF used
06	Missing Endpoint Assessments 
 HbA1c blood sample not collected or insufficient/deficient at baseline or Week 26

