11.6.3.2. Extent of Missing Primary Analysis Data

Missing data is expected to arise mainly from subjects missing complete visits. The amount of missing data for those baseline covariates included in the statistical analysis is expected to be none or at worst minimal. If it should occur, that subject will effectively be lost to analysis. Missing data for HbA1c between two non-missing visits will be considered missing at random (intermediate missing data).

In this study, subjects who withdraw from treatment will stay in the study. In the eCRF, the reason for treatment discontinuation and the reason for withdrawal from the study are collected separately. Whenever the HbA1c value at Week 26 is missing (end of the study), the reason can be determined based on available data in these two locations. The reason for missing data can be classified as lost to follow-up or withdrawal of consent or investigator discretion.

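### The SAP defines the per-protocol population in two conflicting ways, and one of them can let subjects who stopped study drug into Supportive analysis 3

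*SAP*

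**What the plan says.** - **SAP Section 4 (population table):** the per-protocol population is given as "Comprise of all randomized subjects who complete study procedures through Week 26 and are compliant with the protocol". Protocol 9.3.1 has the same condition: those "who complete study procedures through Week 26 and are compliant with the protocol". Neither mentions being on drug.
- **SAP Section 4.1:** the population is those "who complete study procedures on treatment through Week 26 and are compliant with the protocol". SAP 2.1, which lists departures from the protocol's analysis plan, does not mention this one.
- **Follow-up after stopping:** SAP 11.6.3.2 says that "subjects who withdraw from treatment will stay in the study". Protocol 5.5.1.1 and Table 5 bring these subjects back every four weeks and require the Week 26 visit, with HbA1c measured. SAP Appendix 3 assigns HbA1c records to visits in the same way whether or not the subject is still on drug.
- **Dosing criterion:** SAP Appendix 1 lists failure to receive at least "80% of planned medication" as a possible exclusion, to be judged case by case. Stopping treatment is not itself on the list.
- **Compliance formula:** SAP 6.6 defines compliance as "total number of doses administered divided by total number of doses expected over all available scheduled visits on treatment" and sets 80% as the acceptable level.
- **Use:** Supportive analysis 3 (SAP 7.1.1.2) fits the primary MMRM, without imputation, in this population. The data described for that model in SAP 7.1.1.1 include values after discontinuation.

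**The concern.** Two programmers working from this SAP could build different per-protocol populations. A subject who stops drug at Week 8 and attends Week 26 satisfies the Section 4 and protocol wording on procedures and fails the Section 4.1 wording. Stopping is allowed by the protocol, so the requirement to be compliant with the protocol need not exclude that subject either.

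A per-protocol analysis in a non-inferiority trial is read as evidence about subjects who took the treatment. If it contains subjects off drug in both arms, their Week 26 values carry little information about the formulations and can draw the arms together.

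**Working it through.** **1. Do the definitions select different people?** Yes. They differ only in the on-treatment condition, and the trial deliberately keeps subjects who fail that condition under observation to Week 26.

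**2. Does the 80% criterion close the gap?** Dosing is weekly at Weeks 0 to 25 (SAP 6.6), so 26 doses are planned, and 0.80 × 26 = 20.8.

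- If planned medication means all 26 doses, a subject needs at least 21 (21/26 = 80.8%; 20/26 = 76.9%). A Week 8 stopper has 8 or 9 doses (8/26 = 31%; 9/26 = 35%) and meets the exclusion criterion.
- If the SAP 6.6 denominator applies, the same subject with 8 of 8 doses at visits on treatment scores 100% and stays in.
- Even with 26 as the denominator, a subject dosed at Weeks 0 to 20 has 21 doses and passes while off drug afterwards. The 80% rule therefore does not replace the on-treatment condition.

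Appendix 1 does not say which denominator it uses, and either way exclusion is a matter of judgement.

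**3. The plan's own sample-size figure.** Inputs from SAP 11.12.1: margin 0.4, SD 1, true difference 0, one-sided alpha 0.025, 133 per arm. The normal approximation gives 132 per arm for 90% power. The noncentral t distribution at 133 per arm gives 90.1%. The stated 90% is reproduced.

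**4. Effect of equal stopping.** Let *f* be the share of the per-protocol population off drug at Week 26, the same in both arms, with no difference between arms once off drug. Then

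observed difference = (1 − *f*) × on-drug difference.

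The documents do not give *f*; 2% to 13% is assumed. Take an on-drug difference of 0.40, SD 1 and 133 per arm, with the upper confidence bound read against 0.4:

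| *f* | Observed difference | Chance of showing non-inferiority |
|---|---|---|
| 0 | 0.400 | 2.5% |
| 2% | 0.392 | 2.9% |
| 5% | 0.380 | 3.6% |
| 10% | 0.360 | 5.1% |
| 13% | 0.348 | 6.2% |

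With 110 per arm, in case the population is smaller, the last four chances are 2.9%, 3.5%, 4.8% and 5.8%.

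**5. Effect of unequal stopping.** Let *M* be the lyophilized effect against placebo, fully lost off drug, and *D* the on-drug difference:

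observed difference = (1 − *f*liquid)(−*M* + *D*) + (1 − *f*lyo)*M*.

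Take *M* = 0.75, the smaller limit of the interval (−1.04, −0.75) in SAP 11.12.1.

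- 13% liquid, 5% lyophilized, *D* = 0.40: 0.87 × (−0.35) + 0.95 × 0.75 = 0.408; chance of showing non-inferiority 2.1%.
- Same shares, *D* = 0: 0.87 × (−0.75) + 0.95 × 0.75 = 0.06; power falls from 90.1% to 78.9%.
- 5% liquid, 10% lyophilized, *D* = 0.40: 0.95 × (−0.35) + 0.90 × 0.75 = 0.3425; chance 6.8%.

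The direction therefore depends on which arm loses more subjects from treatment.

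**The case against.** The best defence is that SAP Section 4 does not stand alone. The same table cell says that "Protocol deviations that would exclude subjects from the PP population are defined in Section 4.1" and in Appendix 1, and Section 4.1 carries the on-treatment condition. Read together, early stoppers are probably meant to be out. On its most natural reading the 80% criterion refers to all planned doses and would catch a Week 8 stopper. SAP 4.1 has deviations reviewed before unblinding, so the discretion would not be exercised with results in hand. The SAP expects few discontinuations.

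Most of this is fair, and it rules out reading the plan as certainly admitting off-drug subjects: admission is possible, not established. It does not remove the conflict. The cross-reference concerns protocol deviations, and stopping drug is not listed as one. Following it leads to a second definition, with nothing saying which prevails. The natural reading of the 80% criterion competes with the only compliance formula that the SAP supplies, which comes with the same 80% threshold.

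A reader might also infer that the Section 4 wording always favours non-inferiority. The documents do not support that. It holds if stopping is similar in both arms, which the SAP expects. But Protocol Table 2 says that the liquid product's lower pH and larger 50 mg volume may alter injection site reactions, so more stopping on liquid is plausible and would push the other way.

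Nor is the per-protocol analysis the only guard against off-drug convergence. Supportive analysis 2 excludes data after rescue and discontinuation. An optional sensitivity analysis in SAP 11.6.3.4 drops off-treatment data and imputes Week 26 under the non-inferiority null.

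**Conclusion.** The concern holds as a minor inconsistency. The SAP contains two per-protocol definitions, and the one that matches the protocol can admit off-drug subjects to Supportive analysis 3. The possible dilution is modest and rests on three assumptions: an off-drug share that the documents do not state, equal stopping in the two arms, and no difference between arms off drug. At the low end of the assumed range it is close to negligible.

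It would be wrong to infer that the trial's conclusion is at risk. Non-inferiority is decided on the ITT multiple-imputation analysis, which does not use this population, and Protocol 9.3.1 makes the per-protocol set optional support. What is affected is the meaning and reproducibility of one pre-specified supportive result.

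**What to change.** Before unblinding:

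1. Put the Section 4.1 condition, "complete study procedures on treatment through Week 26 and are compliant with the protocol", into the SAP Section 4 table so that there is one definition.
2. List this in SAP 2.1 as a change from Protocol 9.3.1.
3. For the Appendix 1 80% criterion, compute compliance as doses received out of the 26 planned weekly doses (Weeks 0 to 25), and apply it as a fixed rule instead of case by case. The SAP 6.6 formula can remain for the descriptive compliance summaries, provided that the two are labelled as different.

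The cost is a few lines of SAP text and a slightly smaller supportive population. The primary analysis and data collection do not change.

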4.1. Protocol Deviations

- Significant protocol deviations (including deviations related to study inclusion/exclusion criteria, conduct of the trial, subject management or subject assessment) will be summarised by category and standard text description.
- Per-Protocol population is defined as all randomized subjects randomly assigned to treatment who complete study procedures on treatment through Week 26 and are compliant with the protocol. Significant deviations which result in exclusion from the Per-Protocol population will also be listed. (Please refer to [Appendix 1](#): Protocol Deviation Management and Definitions for Per Protocol Population).
- Protocol deviations will be tracked by the study team throughout the conduct of the study in accordance with the Study Deviation Rules document.

- Data will be reviewed prior to unblinding and freezing the database to ensure all significant deviations which may lead to exclusion from the Per-Protocol population are captured and categorised on the protocol deviations dataset.
- This dataset will be the basis for the summaries and/or listings of protocol deviations.
- All protocol deviations regardless of significance will be listed.
- A separate summary and listing of all inclusion/exclusion criteria deviations will also be provided. This summary will be based on data as recorded on the inclusion/exclusion page of the eCRF.

